1.2 Objectives

Primary: To determine the efficacy of lenalidomide and prednisone in combination in patients with MF, in achieving objective improvements in disease status: complete and partial response, hematological improvement.

Secondary: to determine the safety of lenalidomide and prednisone in combination, in patients with MF.

Tertiary: To examine pertinent morphological, biological, and molecular characteristics of MF in patient samples during therapy with lenalidomide and prednisone.

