The course of the disease is highly variable. Median survival from time of diagnosis ranges from 3 to 6 years; survival rates at 2 and 5 years are 68% and 40%, respectively. Progressive marrow failure, transformation into acute myeloid leukemia, and portal hypertension lead to demise.

Various prognostic models have been devised, with only hemoglobin at diagnosis a consistent prognostic factor among several studies. Other parameters included constitutional symptoms, thrombocytopenia, and percentage of WBC precursors.

Lille Scoring System [Hemoglobin < 10 gm/dL, WBC < 4 or > 30 x 10⁹/L]

No. of Adverse Prognostic Features	Risk Group	Median Survival (months)
0	Low	93
1	Intermediate	26
2	High	13

Age of the patient and abnormal karyotype are two additional prognostic features. The median survival of young, low-risk patients can range from 13 to 15 years. Overall median survival is estimated between 3 and 6 years with infections, thrombosis and/or hemorrhage, and transformation to leukemic phase frequently leading to death. Patients without any adverse features may survive as long as 10 years, whereas those with any two of these features have an expected survival less than 3 years.

No standard therapy exists for MF. Hydroxyurea is the most commonly used agent in the proliferative phases of the disease. Interferon-alpha had yielded hematologic responses and reductions in splenomegaly (definitions varying among studies) in 30% to 50% of patients, especially those with proliferative phase, however, this agent tends to be poorly

tolerated. Agents used for the management of anemia include androgens and/or erythropoietin. Splenectomy and/or splenic irradiation have been used to manage symptomatic splenomegaly. Splenectomy has been associated with risk of leukemia transformation in some series, and splenic irradiation can result in severe myelosuppression.

No medical therapy has been proven to prolong overall survival for these patients. Patients with an intact quality of life and no threatening hematologic abnormalities, such as erythrocytosis or thrombocytosis, have usually been considered to not require any therapy; however, new therapeutic modalities are currently being considered in determining treatment indications.

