5.5 Concomitant Therapy

All medications (prescription and non-prescription), treatments and therapies taken from the first day of study through the end of study, must be recorded on the source documents.

The use of filgrastim (G-CSF) for subjects in this study is permitted when used to treat neutropenia secondary to therapy. Erythropoietin therapy is not allowed. Subjects should receive full supportive care, including transfusions of

blood products, antibiotics and antiemetics and prophylactic treatment for potential hypersensitivity reactions and tumor lysis syndrome when appropriate.

Prophylactic Anticoagulation:

Lenalidomide increases the risk of thrombotic events in patients who are at high risk or with a history of thrombosis, in particular when combined with other drugs known to cause thrombosis. When lenalidomide is combined with other agents such as steroids (e.g. dexamethasone, prednisone), anthracyclines (Doxil, adriamycin) and erythropoietin the risk of thrombosis is increased. Consideration should be given to the use of aspirin (81 or 325 mg) or some other form of prophylaxis as deemed appropriate. Low molecular weight heparin may be utilized in patients that are intolerant to aspirin. Coumadin should be used with caution and close monitoring of INR is required.

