6.0 CRITERIA FOR RESPONSE AND TOXICITY

Standard response criteria will be applied in this study. These criterias have been used in all our studies in the last 10years including the lenalidomide single agent study.

CR = Absence of signs or symptoms of the disease.

- WBC between 1 to $10 \times 10^9/L$ with no peripheral blasts, promyelocytes, or myelocytes, and with normalization of bone marrow (< 5% blasts in normocellular or hypercellular marrow, irrespective of marrow fibrosis).

- Resolution of pretreatment cytopenias:
 - ANC $\geq 1.5 \times 10^9/L$ without G-CSF or GM-CSF.
 - Hb >12.0 gm/dl (11.0 gm/dl for females) without erythropoietin or transfusion support.
 - PLT $> 100 \times 10^9/L$ without growth factor or transfusion support.

- Resolution of pretreatment leukocytosis and/or thrombocytosis: (without the use of hydroxyurea and/or anagrelide).
 - WBC $< 10 \times 10^9/L$ without peripheral blasts, promyelocytes, or myelocytes
 - PLT $> 100 \times 10^9/L$ but less than $450 \times 10^9/L$

- Resolution of organomegaly (splenomegaly or hepatomegaly) on physical exam

PR = Improvement in at least 2 of the parameters (if abnormal) listed below:

- Increase of ANC by $\geq 50\%$ and to $> 1.0 \times 10^9/L$ without G-CSF or GM-CSF
- Increase of Hb by ≥ 2 g/dL, if below 10 g/dL before therapy, without erythropoietin or transfusion support.
- Increase of PLT by $\geq 50\%$ and to $> 30 \times 10^9/L$ without growth factor or transfusion support.
- Resolution of pretreatment leukocytosis to WBC $< 10 \times 10^9/L$, without hydroxyurea
- Resolution of pretreatment thrombocytosis to PLT $> 100 \times 10^9/L$ but less than $450 \times 10^9/L$, without hydroxyurea and anagrelide
- Decrease in transfusion requirements by at least 50% without erythropoietin support.
- Reduction of splenomegaly by $\geq 50\%$ by palpation, without hydroxyurea
- Reduction of marrow blasts by $\geq 50\%$, without hydroxyurea
- Reduction of marrow or blood macrocytes by $\geq 50\%$, without hydroxyurea

HI = Improvement in at least 1 of the parameters (if abnormal) listed above under PR

In addition, we will attempt to validate in this study, recently published response criteria developed by the international working group for myelofibrosis. These criteria have not yet been used in any clinical study.

Complete remission (CR): Requires all of the following in the absence of both transfusion and growth factor support;

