- Complete resolution of disease-related symptoms and signs including palpable hepatosplenomegaly.
- Peripheral blood count remission defined as hemoglobin > 11 g/dL, platelet count $\geq 100 \times 10^9/L$, and absolute neutrophil count $\geq 1.0 \times 10^9/L$.
- Normal leukocyte differential including disappearance of nucleated red blood cells and immature myeloid cells in the peripheral smear, in the absence of splenectomy.*
- Bone marrow histological remission defined as the presence of age-adjusted normocellularity, < 5% myeloblasts, and an osteomyelofibrosis grade of ≤ 1 .**

Partial remission (PR): Requires all of the above criteria for CR except the requirement for bone marrow histological remission. However, a repeat bone marrow biopsy is required in the assessment of PR and may or may not show favorable changes that do not however fulfill criteria for CR.

Clinical improvement (CI): Requires one of the following in the absence of both disease progression (as outlined below) and CR/PR assignment (*CI response is validated only if it lasts for ≥ 8 weeks*).

- A ≥ 2 g/dL increase in hemoglobin level or becoming transfusion independent (applicable only for patients with baseline hemoglobin level of < 10 g/dL).[§]
- Either a $\geq 50\%$ reduction in palpable splenomegaly of a spleen that is ≥ 10 cm at baseline or a spleen that is palpable at > 5 cm at baseline becomes not palpable.^{§§}
- A $\geq 100\%$ increase in platelet count and an absolute platelet count of $\geq 50,000 \times 10^9/L$. (applicable only for patients with baseline platelet count of < $50 \times 10^9/L$).
- A $\geq 100\%$ increase in ANC and an ANC of $\geq 0.5 \times 10^9/L$ (applicable only for patients with baseline absolute neutrophil count of < $1 \times 10^9/L$).

Progressive disease: Requires one of the following;[¶]

- Progressive splenomegaly that is defined by the appearance of a previously absent splenomegaly that is palpable at > 5 cm below the left costal margin or a $\geq 100\%$ increase in palpable distance for baseline splenomegaly of 5-10 cm or a $\geq 50\%$ increase in palpable distance for baseline splenomegaly of > 10 cm.
- Leukemic transformation confirmed by a bone marrow blast count of $\geq 20\%$.
- An increase in peripheral blood blast percentage of $\geq 20\%$ that lasts for ≥ 8 weeks.

Stable disease: None of the above.

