9.0 STATISTICAL CONSIDERATIONS

The primary objective of phase II of this study is to assess efficacy in terms of the objective response rate (complete and partial response, and clinical improvement) with lenalidomide and prednisone in patients with MF. The MinMax two-stage design proposed by Simon will be implemented. Sample size and decision criteria are chosen to reduce the expected accrual if the treatment

is ineffective in regard to response relative to having no interim stopping rule. The target response rate is 35%. A response rate of 20% or less will be considered unacceptable and treatment with the therapy will be discontinued. Given the response rates stated above, if the probability of inappropriately accepting a poor therapy is 10%, a total sample size of 41 patients will result in 80% power.

In the first stage of the design, a total of 22 patients will be enrolled and the study will be put on hold to assess response. If four or fewer patients respond to the combination therapy, after being treated for 6 months, then the study will be terminated and the therapy will be declared ineffective. However, as soon as 5 or more patients respond to the lenalidomide, an additional 19 patients will be enrolled to complete the study.

After a total of 41 patients have been enrolled into the study, if eleven or fewer patients respond to the therapy, the therapy will be declared ineffective. However, if greater than 11 patients respond to the therapy, the therapy will be considered efficacious. The probability of early termination due to unacceptable response rate is 54%.

Descriptive statistics will be utilized to assess response, time to response, and response duration. Responses will be categorized as the best response achieved during the course of the study. Time to response is defined as the time from start of therapy until the response criteria are fulfilled. Response duration will be defined as the time from response until relapse (progressive disease) or death.

The safety analysis will include subjects who are enrolled to treatment and take at least one dose of study medication. Toxicity will be graded according to the NCI criteria. Descriptive statistics will be used to describe adverse events related to the study drug. Adverse events will be listed and tabulated.

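### If clinical improvement is the primary endpoint, a haemoglobin rise on transfusion or spleen shrinkage on other myelofibrosis therapy can count as response, and the plan has no scoring rule to prevent it

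*Combined protocol and SAP*

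**What the plan says.** **Which rate is tested.** Section 9.0 defines the primary endpoint as the "objective response rate (complete and partial response, and clinical improvement"). Section 1.2 words the primary objective as "objective improvements in disease status: complete and partial response, hematological improvement". Haematological improvement (HI) belongs to the standard criteria in Section 6.0, which are to be applied in this study. Clinical improvement (CI) belongs to the working-group criteria, which Section 6.0 adds as a validation exercise.

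**Working-group set.** Complete remission "Requires all of the following in the absence of both transfusion and growth factor support". Partial remission inherits this, because it takes over the complete-remission criteria apart from marrow histology. CI has its own header, which asks only that there be no progression and no complete or partial remission, with a duration of at least 8 weeks. Its haemoglobin item is a rise of at least 2 g/dL, that is, an "increase in hemoglobin level or becoming transfusion independent (applicable only for patients with baseline hemoglobin level of < 10 g/dL"). Its spleen item names no excluded treatment.

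**Standard set.** The haemoglobin item excludes erythropoietin and transfusion. The spleen item asks for a reduction of at least 50% "by palpation, without hydroxyurea".

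**Other therapy on study.** Section 5.5 allows transfusion as supportive care and G-CSF for treatment-related neutropenia, and says "Erythropoietin therapy is not allowed". Section 4.2 bars other MF therapy only in the 28 days before lenalidomide starts. Section 5.10 does not list the start of another MF therapy as a reason to discontinue. Section 9.0 scores the best response over the course of the study.

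**The concern.** The trial has one arm, and its decision rests on a count of responders: at least 5 of 22 to continue and at least 12 of 41 to declare efficacy. There is no control group in which the effect of supportive or added treatment would also appear. If such an effect is scored as response, it adds to the count and moves the decision towards efficacy.

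The treatments concerned are ordinary ones in this disease. Section 2.1 states: "Agents used for the management of anemia include androgens and/or erythropoietin". It also states: "Splenectomy and/or splenic irradiation have been used to manage symptomatic splenomegaly". It describes hydroxyurea as the most commonly used agent in proliferative disease and reports spleen reductions with interferon. Patients whose disease is poorly controlled are the most likely to receive them. The exclusions written into the standard items show that the authors saw this confounding, but they were not carried into CI.

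**Working it through.** **Step 1: which routes are open under each criteria set.**

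| Route to a scored response | Working-group CI | Standard HI/PR |
|---|---|---|
| Hb rise of at least 2 g/dL on transfusion | open | excluded |
| Hb rise on erythropoietin | not excluded by the item, but barred on study by 5.5 | excluded |
| Hb rise on androgens | open | open |
| Spleen reduction on hydroxyurea | open | excluded |
| Spleen reduction on interferon or after irradiation | open | open |
| Becoming transfusion independent while still transfused | impossible | not an item |
| Splenectomy | hepatomegaly replaces spleen size (footnote) | not addressed |
| Neutrophil rise on G-CSF | not practical: item needs baseline ANC < 1, entry requires ≥ 1 (× 10⁹/L) | excluded |

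The CI platelet threshold is printed as 50,000 × 10⁹/L, which cannot be reached, so that item is left out.

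Two illustrations under CI. A patient with baseline Hb 7.5 g/dL who is held at 9.5 g/dL by transfusion for 8 weeks has a rise of 9.5 − 7.5 = 2.0 g/dL and meets the item. A spleen of 12 cm that shrinks to 6 cm on hydroxyurea has fallen by 6/12 = 50% and meets the item.

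**Step 2: reproduce the plan's design.** Inputs from Section 9.0: unacceptable rate 20%, target 35%, stage 1 n = 22 (stop at 4 or fewer), total N = 41 (ineffective at 11 or fewer). With X₁ ~ Bin(22, p) and X₂ ~ Bin(19, p):

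- P(early stop) = P(X₁ ≤ 4)
- P(declare efficacy) = Σ over x from 5 to 22 of P(X₁ = x) · P(X₂ ≥ 12 − x)

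At p = 0.20, the early-stop probability is 0.543 (plan: 54%) and false acceptance is 0.096 (plan: 10%, read as the limit). At p = 0.35, power is 0.804 (plan: 80%). The design figures are correct.

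**Step 3: sensitivity to mis-scoring.** Let m be the share of true non-responders scored as responders because of other treatment. The documents give no value for m, so it is an assumption. The apparent rate is p = 0.20 + 0.80m, and the expected number of extra responders in 41 is 41 × 0.80 × m.

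| m (assumed) | Apparent rate | P(declare efficacy) | Extra responders per 41 |
|---|---|---|---|
| 0 | 20.0% | 9.6% | 0 |
| 2% | 21.6% | 14.8% | 0.7 |
| 3% | 22.4% | 18.0% | 1.0 |
| 5% | 24.0% | 25.2% | 1.6 |
| 10% | 28.0% | 46.6% | 3.3 |

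**Step 4: do other passages close the route?**

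- *Eight weeks' duration.* This removes the effect of a single transfusion, but not of regular transfusion or continued cytoreduction.
- *No progression.* The working-group definition deliberately leaves out worsening cytopenia. A greater transfusion need can count only when it lasts more than 3 months after protocol therapy ends.
- *Transfusion footnote.* Transfusing at Hb ≥ 8.5 g/dL is discouraged, with a clinical exception. It is not a scoring rule.
- *Stop for no response within 6 months (5.10).* Taking 6 months as 26 weeks, 26 − 8 = 18 weeks remain in which other treatment could begin and still yield an 8-week effect. A patient mis-scored as CI would not trigger this stop.

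**The case against.** The strongest reply is that CI may not be the primary endpoint. Section 1.2 uses the standard-set term, and Section 6.0 says that the standard criteria will be applied and that the working-group set is there to be validated. If the standard set governs, transfusion is already excluded for the haemoglobin item and hydroxyurea for the spleen item. This stands, and it narrows the gap to androgens, interferon and spleen-directed procedures. It does not settle the matter, because Section 9.0, which holds the decision rule, says clinical improvement.

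A second reply is that the protocol already restrains the route. Uncontrolled proliferative disease has an in-protocol option in lenalidomide escalation (Section 5.2). The supportive-care list names no cytoreductive or spleen-directed therapy. Stage 1 is worded as response to the combination after 6 months of treatment. A later switch counts only if the course of the study extends past discontinuation, which is undefined. A reader might infer that nothing in the protocol stands in the way of scoring rescue treatment as response. The documents do not support that: these passages, the 8.5 g/dL footnote and the 6-month stop all make the route narrower. None of them is a rule about what may be counted.

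A third reply is that m is applied to all non-responders, although under CI only those with baseline Hb below 10 g/dL or a sufficiently enlarged spleen could qualify. That is fair, and it is a reason to read Step 3 as sensitivity only.

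**Conclusion.** The concern holds in a limited form. Sections 1.2 and 9.0 disagree on the third component of the primary rate. Under the Section 9.0 wording, a transfusion-supported haemoglobin rise and a spleen reduction on other MF therapy both meet the criteria as written. Under the Section 1.2 wording a smaller gap remains. In neither case does response counting stop when other MF therapy begins.

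The size of the effect cannot be derived from the documents. A reader might take 25% or 47% as the trial's real false-positive risk. The text does not support that, because the mis-scored fraction is assumed and no rate of on-study rescue is given. The table shows only that the decision rule is sensitive: fewer than two extra responders in 41 (m = 5%) take the error from 9.6% to 25.2% at a true rate of 20%. Nor can it be inferred that every CI item is open. The transfusion-independence limb and the neutrophil item are not, and splenectomy is not simply scored as a spleen response. The point should be addressed because the remedy is cheap; it does not invalidate the design.

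**What to change.** In Section 9.0:

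1. State which criteria set defines the primary response rate, and align Section 1.2 with it.
2. Add a scoring rule for the 5-of-22 and 12-of-41 counts. An improvement in haemoglobin level or platelet count counts only if it is present without transfusion or growth-factor support. Any improvement counts only if first met before other MF-directed therapy is started (hydroxyurea, anagrelide, interferon, androgen, erythropoietin, splenectomy, splenic irradiation). Patients who start such therapy before responding stay in the denominator as non-responders.
3. If the standard set is chosen, apply the transfusion clause to the haemoglobin and platelet items only. The separate item for a fall of at least 50% in transfusion requirement would otherwise lose its meaning.

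Leave the working-group definitions in Section 6.0 as published, so that the validation analysis still tests them.

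The rule concerns scoring and does not restrict care. It needs no new data, since Section 5.5 already requires concomitant therapies to be recorded, and it leaves N and the boundaries unchanged. The costs are a slightly lower observed response rate and slightly less comparability with the earlier single-agent lenalidomide study, which used the standard criteria without this rule.

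### The working-group clinical-improvement platelet item in Section 6.0 carries a 1000-fold unit error and, read literally, cannot be met

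*Combined protocol and SAP*

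**What the plan says.** Section 6.0 contains two sets of response criteria.

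- **Standard set (CR, PR, HI).** The section opens by saying that this set will be applied. Its platelet item reads "Increase of PLT by $\geq 50\%$ and to $> 30 \times 10^9/L$ without growth factor or transfusion support". One such item is enough for HI and two are needed for PR. Where thrombocytosis must resolve, the target is above 100 x 10^9/L "but less than $450 \times 10^9/L".
- **Working-group set (CR, PR, CI).** This set is introduced as an addition that the study will try to validate. CI can be met through hemoglobin, spleen, platelets or neutrophils, and must last at least 8 weeks. The platelet item requires "A $\geq 100\%$ increase in platelet count" together with "an absolute platelet count of $\geq 50,000 \times 10^9/L", and is "applicable only for patients with baseline platelet count of < $50 \times 10^9/L". CR and PR in this set use "hemoglobin > 11 g/dL, platelet count $\geq 100 \times 10^9/L".

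Section 1.2 builds the primary objective on complete response, partial response and hematological improvement. Section 9.0 instead describes the primary measure as the "objective response rate (complete and partial response, and clinical improvement", and applies a two-stage rule: stop at 4 or fewer responders of 22, and declare the therapy ineffective at 11 or fewer of 41.

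**The concern.** The two limits in the CI platelet bullet are printed in the same unit but sit three orders of magnitude apart. The likeliest cause is a count per microlitre joined to the x 10^9/L unit. The line defines an outcome; it is not background.

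Two uses could be affected. The first is the validation of the working-group criteria, which Section 6.0 says no clinical study has yet used. With an unreachable item, that exercise would show no platelet CI by construction. The second is the primary decision. The term clinical improvement is defined only in the working-group list, and Section 9.0 uses that term. If Section 9.0 means that category, a patient who improves on platelets alone would not be counted. Such patients can enrol: Section 4.1 sets no minimum platelet count, and Section 5.0 provides for patients who start below 100 x 10^9/L.

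**Working it through.** **1. Scale of the threshold** (all values in x 10^9/L)

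| Comparator | Where | 50,000 / comparator |
|---|---|---|
| 50, baseline limit in the same bullet | 6.0, CI | 1000 |
| 100, CR/PR platelet level | 6.0, working-group set | 500 |
| 450, upper platelet limit | 6.0, standard set | 111 |
| 500, thrombocytosis | 2.1 | 100 |

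Rise needed under the literal threshold: from a baseline of 10, 50,000/10 = 5000-fold; from 49, 50,000/49 = about 1020-fold. The same bullet asks otherwise only for a doubling.

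Unit conversion: 50 x 10^9 per litre / 10^6 microlitres per litre = 50,000 per microlitre. The digits 50,000 are therefore right for a count per microlitre and wrong for x 10^9/L.

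**2. The item with the unit corrected**

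Required count = max(2 x baseline, 50). For baselines of 10, 20, 25, 30 and 40 this gives 50, 50, 50, 60 and 80. All are reachable.

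**3. One patient under each rule**

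Take a patient who goes from 25 to 55 without growth factor or transfusion support, sustained for 8 weeks, with no disease progression.

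- Standard set: the rise is (55 - 25)/25 = 120%, at least 50%, and 55 > 30. HI is scored.
- CI, corrected: 55 >= max(50, 50). The item is met.
- CI, as printed: 55 < 50,000. The item is not met.

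The misprint thus changes the result only under the CI platelet line.

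**4. The plan's own design figures**

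Inputs from Section 9.0: n1 = 22, r1 = 4, n = 41, r = 11, p0 = 0.20, p1 = 0.35.

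- Probability of early termination = P(X1 <= 4), with X1 ~ Bin(22, p).
- Probability of declaring efficacy = sum over x = 5 to 22 of P(X1 = x) x P(X2 >= 12 - x), with X2 ~ Bin(19, p).

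At p = 0.20, early termination is 0.543 and type I error 0.096. At p = 0.35, power is 0.804. The stated 54%, 10% and 80% reproduce, and correcting the unit changes none of them.

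**5. Conditional illustration**

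This applies only if working-group CI feeds the primary rate and the line is applied literally. Suppose the true rate is 35% and k expected responders in 41 are platelet-only. The scored rate is then 0.35 - k/41.

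| k (assumed) | Scored rate | Exact power |
|---|---|---|
| 0 | 35.0% | 80.4% |
| 1 | 0.35 - 0.0244 = 32.6% | 70.5% |
| 2 | 0.35 - 0.0488 = 30.1% | 58.3% |

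The documents give neither the share of patients below 50 x 10^9/L nor a platelet-only response rate, so k is an assumption. If HI is the primary component, k = 0.

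**The case against.** The strongest reply is that this is an obvious misprint with little practical reach. The bullet shows its own scale through the baseline limit and the doubling, and the plan's other platelet values are in tens or hundreds x 10^9/L. An assessor would probably read 50. The faulty line also sits in the additional set, while the standard set is the one to be applied and Section 1.2 names HI. On that reading the decision counts do not move at all.

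Most of this stands. A reader might infer from the bullet that platelet responses can never be scored in this trial. The documents do not support that: the standard platelet item is reachable and alone gives HI, and working-group CR and PR use a reachable 100 x 10^9/L. A reader might also infer from Section 9.0 alone that platelet-only responders are certain to drop out of the 5/22 and 12/41 counts. That does not follow either, because Sections 1.2 and 6.0 point to HI. The power figures for one or two lost responders rest on no rate in the plan. With few patients likely to be eligible for this item, two lost responders would be towards the unfavourable end.

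What does not stand is that nothing needs doing. The printed figure is wrong in a definition that the study intends to test, and a scoring form built from the text would reject every case.

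**Conclusion.** The threshold is wrong as written, by a factor of 1000, and the CI platelet item cannot be met if read literally. The certain consequence of literal use is confined to the working-group criteria: their validation would record no platelet CI, whichever set is primary.

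An effect on the primary analysis is conditional on two things: that clinical improvement in Section 9.0 means the working-group category, and that the printed figure is applied. Its size then depends on an unknown number of platelet-only responders. It ranges from nothing to the illustrative falls in power shown above. The sample size, stopping limits and stated error rates are sound.

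This is a minor correction, unless the sponsor confirms that working-group CI is a component of the primary response rate. In that case it should be corrected before any response is scored for the stage 1 decision.

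**What to change.** 1. In Section 6.0, working-group CI, change the absolute platelet threshold to 50 x 10^9/L (50,000/uL), on the scale of the bullet's own baseline limit. Use the corrected value wherever CI is scored, including the working-group relapse rule, which refers back to CI.
2. Reconcile Sections 1.2, 6.0 and 9.0 by stating whether HI (standard set) or CI (working-group set) counts in the primary response rate, and use that one term throughout.
3. If any response has already been scored with the printed figure, rescore the platelet item for patients with baseline below 50 x 10^9/L.

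The first change is one figure and the second a sentence, both of which fit in the next amendment. Correcting the figure leaves the sample size, stopping limits, type I error and power as planned. The choice between HI and CI needs a decision by the sponsor, because the two categories have different thresholds.
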